8.3.5 Primary Efficacy Analysis

Т

The primary efficacy analysis will be conducted using an analysis of variance (ANOVA) model with the percentage change from Baseline to Week 8 in EASI score as the dependent variable and treatment group and the randomization stratification variable as factors.

Missing data for raw EASI data will be imputed from baseline, and percent change from baseline will then be calculated. The	Change

Protocol title: A RANDOMIZED, VEHICLE-CONTROLLED, SAFETY AND EFFICACY STUDY OF EVO101 IN ADULT SUBJECTS WITH ATOPIC DERMATITIS

Sponsor code: EVO101-AD001

code: EPQ1001

Version number: Final 1.0

Date: 17-AUG-2023

Additionally, a box plot will be created with the percentage of change from baseline as the y-axis and the treatment group as the x-axis.

The primary efficacy analysis will be performed on the ITT population. Derivation of the EASI score is described in appendix 10.1.

A sensitivity analysis of the primary endpoint will be conducted in the PP population.

8.3.6 Secondary and Exploratory Analyses

Protocol title: A RANDOMIZED, VEHICLE-CONTROLLED, SAFETY AND EFFICACY STUDY OF EVO101 IN ADULT SUBJECTS WITH ATOPIC DERMATITIS

Sponsor code: EVO101-AD001

code: EPQ1001

Version number: Final 1.0

Date: 17-AUG-2023

Derivations of the following assessments are described in appendix 10.1.

The following summaries and analyses will be conducted:

EASI:

- Summary statistics at baseline, Week 2, Week 4 and Week 8 will be provided by each treatment group as well as for the change and percentage change from baseline. These analyses will also be conducted using the PP population.
- Number and percentage of subjects with EASI-75 at Week 2, Week 4 and Week 8 (defined as a subject with a percentage change from baseline <= - 75). These analyses will also be conducted using the PP population.
- Number and percentage of subjects with EASI-90 at Week 2, Week 4 and Week 8 (defined as a subject with a percentage change from baseline <= - 90).
- A listing with the visit, date of the assessment, score, change and percentage from baseline and the flags of EASI-75 and EASI-90.

IGA:

- Summary statistics at baseline, Week 2, Week 4 and Week 8 will be provided by each treatment group.
- Number and percentage of subjects with IGA response (≥2 points change from baseline (i.e., a change from baseline ≤ -2) at Week 8 and comparisons between treatments will be conducted in the ITT and PP populations.
- Number and percentage of subjects with IGA success (subjects with a score of 0 to 1 who have an improvement of ≥ 2 points, that means a change from baseline ≤ -2) from Baseline at Week 8 and comparison between treatments.
- A listing with the visit, date of the assessment, score, change from baseline and the flags of IGA response and IGA score of 0 to 1 who have an improvement of ≥ 2 points achievement.

BSA:

- Summary statistics at baseline, Week 2, Week 4 and Week 8 will be provided by each treatment group as well as for the change and the percentage change from baseline.
- Comparison between treatments for the change and percentage change from baseline to each visit.
- A listing with the visit, date of the assessment, value, change and percentage change from baseline.

Pruritus-NRS:

• For the assessment of pruritus-NRS:

Protocol title: A RANDOMIZED, VEHICLE-CONTROLLED, SAFETY AND EFFICACY STUDY OF EVO101 IN ADULT SUBJECTS WITH ATOPIC DERMATITIS

Sponsor code: EVO101-AD001

code: EPQ1001

Version number: Final 1.0

Date: 17-AUG-2023

- Day 1 through Day 7 values will be based on the single assessments performed on each subject on that day.
- Baseline, Week 1, Week 2, Week 3, Week 4, Week 5, Week 6, Week 7 and Week 8 values will be based on the average pruritus-NRS score of the 7 days prior to the visit date. Subjects with less than 4 values in the 7 days prior to the visit date will have that visit value considered missing.
- Summary statistics at baseline, Day 1, Day 2, Day 3, Day 4, Day 5, Day 6, Day 7, Week 1, Week 2, Week 3, Week 4, Week 5, Week 6, Week 7 and Week 8 will be provided by each treatment group as well as the change and percentage of change from baseline.
- Comparison between treatments in the change and percentage change from baseline to each visit will be conducted in the ITT and PP populations.
- Number and percentage of subjects achieving a 4-point improvement in the pruritus-NRS score from Baseline to Week 8 in subjects who had an average maximum pruritus-NRS score of at least 4 at Baseline. Comparisons between treatments will be made in the ITT and PP populations.
- A listing with the visit, date of the assessment, score, change and percentage from baseline and the flags of 4-point improvement achievement.

Pharmacokinetics:

Plasma levels of EVO101 will be evaluated by:

- Summary statistics at baseline, Week 2, and Week 8 will be provided for the active treatment group.
- A listing with the visit, date of the assessment and value.

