7.1. Inclusion Criteria

Subjects must meet all of the following criteria to be eligible for study participation:

- 1. Signed informed consent.
- 2. Willing and able to comply with the study visit schedule, procedures, and questionnaires.
- 3. Male or non-pregnant, non-lactating, females, age ≥ 18 years.
- 4. Chronic AD (according to the American Academy of Dermatology Consensus Criteria) that has been present for ≥1 year before the Screening visit.
- 5. Investigator's Global Assessment score of 2 to 3 at Screening and Baseline.
- 6. EASI of 5-20 at screening and baseline.
- 7. BSA of AD involvement, excluding the face and intertriginous areas, of 4% to 12% at Screening and Baseline.
- 8. Application of a stable dose of non-medicated topical moisturizer twice daily for \geq 7 days prior to the Baseline visit and willing to maintain stable dosing during study participation
- 9. Completed electronic diary entries for pruritus for a minimum of 4 of 7 days preceding randomization at the Baseline visit.
- 10. Willing to use effective contraceptive method, if applicable, during study participation and for 30 days following the end of treatment.

For women of childbearing potential: agree to remain abstinent (refrain from heterosexual intercourse) or use a highly effective contraceptive method during the treatment period and for at least 30 days after the last application of study drug.

A woman of childbearing potential is defined as a postmenarcheal female, who has not reached a postmenopausal state (≥ 12 continuous months of amenorrhea with no identified cause other than menopause) and has not undergone surgical sterilization (removal of ovaries and/or uterus).

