8.3 Hypothesis and Statistical Methods

8.3.1 Definitions

Baseline	Baseline value refers to the last non-missing assessment made before or up to the date of the first study drug application at the screening or baseline visit.
	If not possible to obtain a baseline value from the specified visits the unscheduled assessment will be included in the derivation of baseline value.
	Baseline pruritus score is derived based on the prior 7 days of subject diary data, of which at least 4 of the 7 days must be completed.
Date of first study drug	The date of first study drug application will be taken from ePRO.
application	In case ePRO is not available, then the first available date will be taken from the drug accountability.
Relative day	The relative day of an event is derived as:
	Relative day = (Start date) - (Date of first study drug application) + 1
	For events occurring or starting before the date of first study drug application the relative day is derived as:
	Relative day = (Start date) - (Date of first study drug application)
	In this way, there will be no Day 0. Day 1 is the same day as the day of first study drug application, and Day -1 is the day before.
	Relative day will be calculated only for the completed dates.

Protocol title: A RANDOMIZED, VEHICLE-CONTROLLED, SAFETY AND EFFICACY STUDY OF EVO101 IN ADULT SUBJECTS WITH ATOPIC DERMATITIS

Sponsor code: EVO101-AD001

code: EPQ1001

Version number: Final 1.0

Date: 17-AUG-2023

Treatment-emergent adverse event (AE)	Treatment-emergent is defined as any AE with an onset on or after the date of the first study drug application:
	TEAE if: (Start AE date) ≥ (Date of first study drug application)
	Derivation of the flag when missing or partial AE dates is specified in section 8.8.
	AEs reported on the same day as first drug administration, associated with abnormal physical examination findings and vital signs, will be identified and manually reviewed by the medical monitor to confirm if the AE(s) will be considered as a treatment-emergent event.
	Additionally, AE(s) reported same day as first drug administration associated with a skin reaction and indicated in the reported term (pre- dose or pre-administration) will not be considered as treatment- emergent.
Change from baseline to	Change from baseline to specific visit will be calculated as:
specific visit	Change to visit X = Value at visit X – Baseline value

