Percentage of change from baseline to specific	Percentage of change from baseline to specific visit will be calculated as:
VISIT	Percentage of change to visit X =
	[(Value at visit X – Baseline value) / (Baseline value)] x 100

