	Note: No additional calculation will be needed for this assessment.
	The value of the IGA score to be used for the analysis will be the corresponding IGA score in the visit schedule: Week 2, 4 and 8. The baseline value is defined in section 8.3.1.
BSA	The BSA assessment estimates the extent of disease or skin involvement with respect to AD and is expressed as a percentage of total body surface. BSA will be determined by the Investigator or designee using the subject palm = 1% rule.
	Note: No additional calculation will be needed for this assessment.
	The value of BSA percentage to be used for the analysis will be the corresponding BSA percentage in the visit schedule: Week 2, 4 and 8. The baseline value is defined in section 8.3.1 Error! Reference source not found. .
Pruritus-NRS	Pruritus will be assessed using a Pruritus Numerical Rating Scale (NRS). The Pruritus NRS is an 11-point scale used by subjects to rate their worst itch severity over the past 24 hours with 0 indicating "No itch" and 10 indicating "Worst itch imaginable." Subject assessments will be captured daily using an electronic diary.
	The value at each visit (Baseline, Week 1, Week 2, Week 3 Week 4, Week 5, Week 6, Week 7 Week 8) will be calculated as the mean of the values of the 7 previous days up to the corresponding visit. If there are less than 4 values in the prior 7 days, the value for that visit day will be set to missing.
	Values at each day (Day 1 through Day 7) will be the corresponding value collected in the day specified. The baseline value is defined in section 8.3.1.
	If more than one assessment is reported in the same day, then it will be taken that one with the worst severity following a conservative approach.

In the case of early withdrawals, a time window will be used for the efficacy assessments mentioned above, to reassign values to the correct visits using the days from baseline as follows.

Visit	Target day	Visit Window (days on treatment)
Visit 2	14	Days from Baseline ≤ 21
Visit 4	28	21 < Days from Baseline ≤ 42
Visit 8	56	42 < Days from Baseline

Statistical Analysis Plan Protocol title: A RANDOMIZED, VEHICLE-CONTROLLED, SAFETY AND EFFICACY STUDY OF EVO101 IN ADULT SUBJECTS WITH ATOPIC DERMATITIS Sponsor code: EVO101-AD001 code: EPQ1001 Version number: Final 1.0 Date: 17-AUG-2023

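### The exploratory comparison of percentage change in pruritus-NRS has no readable baseline minimum or zero-denominator rule, so it is undefined at a baseline of 0 and unstable well below 1

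*SAP*

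**What the plan says.** - **Comparison.** SAP 8.3.6, under Pruritus-NRS: "Comparison between treatments in the change and percentage change from baseline to each visit will be conducted in the ITT and PP populations". Protocol 3.1 and SAP section 4 list the Week 8 percentage change among the exploratory efficacy endpoints.
- **Formula.** SAP 8.3.1 defines percentage change for every measure with the baseline as denominator: "Value at visit X – Baseline value) / (Baseline value)] x 100". It gives no instruction for a baseline of 0.
- **Baseline value.** Also in SAP 8.3.1: "Baseline pruritus score is derived based on the prior 7 days of subject diary data, of which at least 4 of the 7 days" (the entries needed for a baseline value). The scale runs from 0 to 10, and 0 (no itch) is a valid answer (Protocol 11.4, SAP 10.1).
- **Entry.** For itch, Protocol 7.1 asks only for "Completed electronic diary entries for pruritus for a minimum of 4 of 7 days preceding randomization at the Baseline visit". Other measures have a floor in the same list: "EASI of 5-20 at screening and baseline", and BSA "of 4% to 12% at Screening and Baseline".
- **Responder analysis.** The 4-point responder bullet in SAP 8.3.6 is limited to a subset: "in subjects who had an average maximum pruritus-NRS score of at least 4 at Baseline". The percentage-change bullet just before it carries no limit.

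**The concern.** A percentage change is stable only when its denominator stays clear of zero. Eligibility ensures that for EASI (at least 5) and BSA (at least 4%), but not for itch. IGA, EASI and BSA grade visible signs and extent, so their floors do not bound the itch a subject reports.

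Two things follow. A subject with a baseline weekly mean of 0 has no percentage change and would drop out of a comparison labelled ITT, with no stated rule or count. A subject just above 0 can record a change of several hundred percent from a small absolute worsening. The same small denominator is reused at every visit, so the distortion can recur across the table.

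At stake is whether one exploratory itch comparison can be read at face value, since its mean and SD could be driven by the subjects with the least itch.

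**Working it through.** **The plan's own figure.** The only sizing statement (Protocol 15.8) concerns EASI: 59 per arm, a 30-point difference, SD 50, one-sided alpha 0.05, power above 90%. Normal approximation: 30 / (50 × √(2/59)) = 3.26; 3.26 − 1.645 = 1.61; power 94.7%. The statement reproduces. Nothing comparable is given for pruritus-NRS.

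**Smallest baselines.** The baseline is a mean of 4 to 7 whole-number scores. It can be 0, and its smallest non-zero value is 1/7 = 0.143 with seven entries or 1/4 = 0.25 with four.

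**One subject's effect on an arm.** Assumptions not in the documents for pruritus: the other 58 subjects average −30%, with SD 40 (SD 50, the EASI value, for comparison). With p the subject's percentage change:
- shift in arm mean = (p + 30) / 59
- arm SD = √{[57 × SD² + (58/59) × (p + 30)²] / 58}

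| Baseline → Week 8 | p | Shift (points) | Arm SD (from 40) | Arm SD (from 50) |
|---|---|---|---|---|
| 0 → any | undefined | – | – | – |
| 1/7 → 3 | +2000% | 34.4 | 267 | 269 |
| 0.25 → 2 | +700% | 12.4 | 103 | 107 |
| 0.5 → 3 | +500% | 9.0 | 80 | 85 |
| 1 → 4 | +300% | 5.6 | 58 | 66 |
| 1 → 3 | +200% | 3.9 | 50 | 58 |

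For example, 0.25 → 2: (2 − 0.25)/0.25 = 700%; 730/59 = 12.4; √{[57 × 1600 + (58/59) × 730²]/58} = 103.

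**Effect on a test.** Assume arm means of −60% (active) and −30% (vehicle), SD 50, 59 per arm and an ordinary comparison of means. Without an extreme value, t = 3.26 and one-sided p = 0.0007. Replacing one active-arm subject:
- 1/7 → 3: active mean (58 × −60 + 2000)/59 = −25.1; the difference becomes −4.9, so the sign reverses; p = 0.55
- 0.25 → 2: active mean (58 × −60 + 700)/59 = −47.1; difference 17.1; p = 0.14
- 0.5 → 3: difference 20.5; p = 0.061
- 1 → 3: difference 25.6; p = 0.007

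Only the most extreme of these reverses a 30-point difference.

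**With a baseline of at least 4.** The largest possible value is (10 − 4)/4 = +150%. One subject then moves a 59-subject arm (others at −30%) by at most 180/59 = 3.1 points. Fewer subjects would remain, so the bound is 180/m for m subjects per arm, for example 4.5 points if m were 40. No zero denominator can occur. For comparison, EASI from 5 to 20 is +300%, or 330/59 = 5.6 points.

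**The case against.** **Unreadable text.** The opening of SAP 8.3.6 and the list of changes in 8.1 cannot be read in the public copy. The version history shows that 8.3.6 holds rules not visible there, including multiple imputation for pruritus-NRS change and a restriction to participants with baseline and post-baseline data. A low-baseline rule could be among them. This stands: the point is about the readable text. The test for pruritus percentage change is not readable either, and Protocol 15.4.2 assigns ANOVA and ANCOVA to secondary endpoints only. The effect on the arm mean and SD does not depend on the test; the p-values above do.

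**Plausibility.** Each scenario needs a subject with active disease (IGA 2 or 3, EASI at least 5) whose weekly mean of daily worst itch is at or near zero and then rises. No baseline distribution is given, so the frequency is unknown. This also stands.

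**Safeguards.** Absolute change is compared in the same bullet and has no such defect. Medians and ranges are reported (SAP 8.3.2) and individual percentage changes are listed, so an extreme value would be seen. That limits the harm, but detection after unblinding leaves the handling to be chosen with results in view.

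**The cut-off of 4.** In the responder analysis it is there because nobody below 4 can improve by 4 points. A reader might infer that the SAP recognised an unstable denominator in one bullet and forgot it in the next; the documents do not show that. The cut-off is also stricter than stability alone requires, and it narrows a population that SAP section 7 sets as ITT for exploratory efficacy analyses. Both remarks are fair, which is why 4 is offered for convenience and not as the only valid choice.

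**Conclusion.** The point holds as a minor one. On the readable text, a planned exploratory comparison is undefined for an admissible baseline (0) and unstable for baselines well below 1. Under the assumed inputs, one subject going from 0.25 to 2 moves a 59-subject arm mean by 12.4 points and takes the SD from 40 to about 103. From a baseline of 1 the shift is about 4 to 6 points.

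Two stronger readings are tempting. One is that a single low-itch subject would readily reverse the direction of the result. A 12.4-point shift does not reverse a difference of 30 points, the only effect size in the documents and one stated for EASI. Reversal needs a more extreme case, such as 1/7 to 3 with a shift of about 34 points, or a small true difference. The other is that the trial's efficacy conclusion is at risk. It is not: the primary and secondary endpoints do not use pruritus-NRS, and EASI and BSA have entry floors.

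The conclusion rests on the readable text being complete on this point, on a comparison of untransformed means, and on the illustrative -30% and SD 40. Whether any such subject was enrolled cannot be told from the documents.

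**What to change.** First check the unreadable part of SAP 8.3.6. If it already covers zero and low baselines, nothing more is needed. Otherwise add to the pruritus-NRS part of 8.3.6, before unblinding:

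1. Absolute change from baseline in all ITT subjects is the main pruritus comparison.
2. Percentage change is compared only in subjects with a baseline weekly mean of at least 4, the subset already defined for the responder analysis.
3. If all subjects with a non-zero baseline are also shown, they are compared by medians or ranks, and the number excluded for a zero baseline is reported by arm.

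SAP 8.2 already provides for a revised, signed SAP before the blind is broken. The cost is a few sentences and fewer subjects in the percentage-change table, which would then describe only subjects with a baseline itch of 4 or more. No extra data are needed.

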8.3.7 Exposure to Treatment

The extent of exposure to study drug in each treatment group will be summarized by total number of days of exposure, total number of applications, number of missed applications and number and percentage of subjects who are compliant. A subject will be considered compliant with the dosing regimen if the subject applied 80% to 120% of the expected number of applications while enrolled in the study. The compliance categories will be: <80%, [80%-120%] and >120%. Compliance will be summarized additionally as a quantitative variable.

Extent of exposure to study drug will be derived as:

Exposure (days) = (last study drug application date) – (first study drug application date) + 1

Compliance will be derived as:

Actual compliance (%) = (total number of applications / total number of expected applications as per protocol) x 100

Protocol title: A RANDOMIZED, VEHICLE-CONTROLLED, SAFETY AND EFFICACY STUDY OF EVO101 IN ADULT SUBJECTS WITH ATOPIC DERMATITIS

Sponsor code: EVO101-AD001

code: EPQ1001

Version number: Final 1.0

Date: 17-AUG-2023

Handling incorrect exposure data reported

Since the exposure data is collected by an ePRO, the following describes the possible issues that can be found and how to hand them for the analysis.

All the subjects with any of the described issues will be reviewed and confirmed during the DR meeting. Additionally, for subjects with exposure data as described in third issue it will be established a rationale to include/exclude them from PP population during the DR meeting.

8.3.8 Concomitant Medications and Therapy

All concomitant medications/therapies will be classified according to ATC level 3 group text and World Health Organization (WHO) Drug Dictionary preferred name. The medications will be classified into categories Prior and Concomitant based on start date and end date in relation to study drug exposure.

- Prior medication is defined as any medication/therapy strictly taken before the first study drug application.
- Concomitant medication is defined as any medication/therapy which the period between their start dates and end dates coincide with exposure to study drug.

The derivations will be as follows:

A medication will be considered a prior medication if one of the two following conditions are met:

- (End medication/therapy date) < (Date of first study drug application)

Protocol title: A RANDOMIZED, VEHICLE-CONTROLLED, SAFETY AND EFFICACY STUDY OF EVO101 IN ADULT SUBJECTS WITH ATOPIC DERMATITIS

Sponsor code: EVO101-AD001

code: EPQ1001

Version number: Final 1.0

Date: 17-AUG-2023

- (Start medication/therapy date) < (Date of first study drug application) and (End medication/therapy date) = Missing and "Ongoing" option is not ticked in the eCRF.

A medication will be considered as a concomitant medication if one of the two following conditions are met:

- (End medication/therapy date) \geq (Date of first study drug application)
- "Ongoing" option is not ticked in the eCRF.

Derivation of the flag when missing or partial dates is specified in section 8.8.

The concomitant medications will be presented separately by prior and concomitant medications in two summary tables presenting the number and percentage of subjects with at least one occurrence for a preferred name. If a subject has more than one medication, the subject will only be counted once for each medication and timing category, on a preferred name level in each period. The calculation of percentages will be based on the number of subjects within each treatment arm based on the Safety population.

Additionally, a listing by subject for each period (prior and concomitant) will be presented for the SAF including the ATC 3 level, preferred name, reported name, start/end date, ongoing option, dose (units), route, frequency, indication, reason for medication and the associated AE as long as they are available.

